11.2.2.6 Evaluation of Secondary and Exploratory Efficacy Variables

All secondary and exploratory variables listed under [Sections 9.1.2](#) and [9.1.3](#) will be analyzed descriptively for categorical and continuous data, as applicable. For continuous data, the change from baseline will be analyzed in addition to the actual visit values. For categorical data, shift tables or frequency and percentages of patients will be presented as appropriate.

Change in growth (Z-score, SD from P50 standard growth curve) will be analyzed by using one-sample T-test or Wilcoxon signed-rank test as appropriate. Change in growth (height/length for age, weight for age, BMI, and mid-arm circumference) will also be displayed using graphical presentations.

A 95% CI will be calculated for the proportion of patients experiencing surgical bile diversion or liver transplantation or death as well as for the proportion of patients experiencing surgical bile diversion or death or liver transplantation. The upper boundary will be compared to the expected proportion of events, using the event probability estimated from the untreated reference population in an ongoing observational cohort study.

Time to first event, i.e., time to surgical bile diversion or liver transplantation or death, will be explored by descriptive statistics and Kaplan-Meier curves, which also will be used to make a comparison to the NAPPED population. The propensity score matched cohort analysis using inverse probability of treatment weights will be used to match the study patient population to the reference population based on age group and PFIC type.

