11 STATISTICAL EVALUATION

11.1 Sample Size and Power

There is no formal hypothesis testing in this open label study. Sample size for Cohort 1 was determined in Study A4250-005. For Cohort 1, patients will be enrolled following completion or participation of 12 weeks of Study A4250-005. The expected proportion of patients with at least one event, i.e., surgical bile diversion or liver transplantation or death, in untreated patients is expected to be high enough to be able to detect an improvement after A4250 treatment. For the other endpoints, mainly descriptive analyses will be performed.

The proportion of patients with at least one event (i.e., surgical bile diversion or liver transplantation or death), that can be expected in a non-treated population depends on PFIC type and age distribution of the included patients. The expected proportion of patients with events will be calculated for the study population once each patient's age and PFIC type are known, using the probability that a patient will get an event estimated from the reference population in the ongoing observational cohort study, NAtural Course and Prognosis of PFIC and Effect of Biliary Diversion (NAPPED).

As an example, if the expected proportion with at least one event is estimated to be 30% in the study population, and then if the proportion of patients with at least one event during A4250 long-term treatment are shown to be only 10% in the study, the power is approximately 89% to 96% (1-sided test, alpha=2.5%) for a confidence interval (CI) with upper boundary <30% based on a sample size of n=48 to 60. The sample size of 60 patients for Cohort 2 was estimated based on the availability of target patient population to evaluate the therapeutic benefit for those patients.

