11.2 Statistical Methods

11.2.1 Statistical Analysis Sets

Full Analysis Set

The full analysis set (FAS) will consist of all patients who received at least 1 dose of study drug in Study A4250-008. The FAS will be the primary analysis set for all analyses unless otherwise specified.

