11.2.2.2 Missing Data

Missing data will be reported descriptively. In general, imputations of missing observations will not be made. Any additional sensitivity analysis concerning missingness and details regarding handling of missing data will be described in the statistical analysis plan (SAP).

Continued collection of efficacy data for patients who discontinue treatment will be made as far as possible.

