11.2.3 Interim Analysis

Analyses may be performed at select time points throughout the collection of patient data for regulatory requirements and sponsor decision making purposes.

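### The upper-limit comparison with the NAPPED-based expected proportion rests on a simple proportion that makes no allowance for patients whose status at Week 72 is unknown

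*Protocol*

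**What the plan says.** **Estimator.** Protocol section 11.2.2.6 plans: "A 95% CI will be calculated for the proportion of patients experiencing surgical bile diversion or liver transplantation or death". The upper limit is compared with an expected proportion derived from the untreated reference cohort. The sentence names neither a denominator nor a rule for patients not followed to Week 72.

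**Population and missing data.** Section 11.2.1 defines the full analysis set (FAS) as everyone with at least one dose and adds: "The FAS will be the primary analysis set for all analyses unless otherwise specified". Section 11.2.2.2 says: "In general, imputations of missing observations will not be made", and leaves the details to the statistical analysis plan, which is not at hand.

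**Power example.** Section 11.1 supposes "if the expected proportion with at least one event is estimated to be 30% in the study population" and patients with "at least one event during A4250 long-term treatment are shown to be only 10% in the study". It gives 89% to 96% power, at one-sided alpha of 2.5%, for an "upper boundary <30% based on a sample size of n=48 to 60".

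**Event follow-up.** Sections 7.1.1 and 7.2.3 require telephone contact every 3 months after early discontinuation, up to Week 72, to ask about biliary diversion, liver transplantation and the resolution of ongoing adverse events. Death is not named. Section 10.1.2 records no new adverse events after permanent discontinuation. Section 10.1.3 asks for a death report within the study period or within 28 days of the last dose.

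**Companion analysis.** Section 11.2.2.6 also plans Kaplan-Meier curves for time to the same composite, compared with NAPPED.

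**The concern.** A simple proportion is a valid estimate of 72-week risk only if every patient's 72-week status is known. A treated patient with unknown status who stays in the denominator can add no event, so the proportion and its upper limit are too low. The Kaplan-Meier analysis allows for this, but the confidence limit that is set against the reference does not come from it.

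This is the one comparison in the study with a power statement. A limit that is too low makes it easier to conclude that the event proportion on A4250 is below that of untreated patients.

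**Working it through.** **Step 1: reproduce the plan's power.** Inputs from section 11.1: reference 30%, true proportion 10%, n = 48 or 60, two-sided 95% limit. The exact (Clopper-Pearson) upper limit for x events in n is the 0.975 quantile of Beta(x+1, n−x). Find the largest x with a limit below 30%, then take P(X ≤ x) at p = 0.10.

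- n = 48: x ≤ 7, power 89.8%.
- n = 60: x ≤ 10, power 96.6%.

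Both are close to the stated 89% and 96%. The Wilson limit gives 95.4% and 98.5% and the Wald limit 98.1% and 98.5%, so neither matches both ends. The calculation treats each of the n patients as having a known outcome.

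**Step 2: bias of the simple proportion.** The protocol gives no loss rate. Assume a share L of patients leaves with no later event information, exit is uniform over the 72 weeks, the hazard is constant, and exit is unrelated to risk. With true 72-week risk p:

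- λ = −ln(1−p)
- chance that a lost patient's event is seen before exit: c = 1 − p/λ
- expected simple proportion: q = (1−L)·p + L·c

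For p = 0.10: λ = 0.1054 and c = 0.0509.

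- L = 10%: q = 0.090 + 0.0051 = 0.0951, relative bias −4.9%.
- L = 20%: q = 0.080 + 0.0102 = 0.0902, relative bias −9.8%.

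At p = 0.20 the biases are −4.8% and −9.6%. With L = 0 there is none.

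**Step 3: effect on the comparison when the true risk equals the reference.** For p = 0.30, λ = 0.3567 and c = 0.1589. The table gives P(X ≤ 7) for n = 48 and P(X ≤ 10) for n = 60 at the resulting q.

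| Share unobserved | Expected proportion q | n = 48 | n = 60 |
|---|---|---|---|
| 0% | 30.0% | 1.1% | 1.4% |
| 5% | 29.3% | 1.5% | 1.9% |
| 10% | 28.6% | 1.9% | 2.4% |
| 20% | 27.2% | 3.1% | 4.1% |
| 30% | 25.8% | 4.8% | 6.7% |

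The exact limit is conservative (1.1% and 1.4% at full follow-up), and that margin absorbs a loss of up to 10%.

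**Step 4: a single result.** With 6 events in 60 patients the exact upper limit is 20.5%. If 6 event-free patients had unknown status, leaving them out entirely gives 6/54 and a limit of 22.6%. That over-corrects, because it discards the time they were observed. The Kaplan-Meier point estimate would lie between 6/60 = 10.0% and 6/54 = 11.1%.

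**The case against.** **The denominator is inferred.** A reader might take the protocol to say that unobserved time counts as event-free. It does not. The FAS is only a default, and scoring an unobserved patient as a non-event could itself be called an imputation, so excluding or censoring such patients would also fit section 11.2.2.2. The details go to the statistical analysis plan. This stands. What remains is that the protocol chose a simple proportion for the reference comparison, and that estimator cannot use partial follow-up.

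**Stopping treatment does not stop event follow-up.** This also stands. The telephone contacts run to Week 72 and continue even after a diversion or transplantation. The gap is limited to patients who cannot be reached or refuse, and to late deaths. A caller would probably learn of a death, but no item requires it to be recorded.

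**Kaplan-Meier is already planned.** True, and it makes the change cheap. It does not alter the estimator behind the upper limit.

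**Interim analyses.** Section 11.2.3 says: "Analyses may be performed at select time points throughout the collection of patient data for regulatory requirements and sponsor decision making purposes". A reader might infer a large bias at a data cut: with half the patients short of Week 72, Step 2 at p = 0.10 and L = 50% gives about −25%. The protocol does not say that this comparison would be run then, or that such patients would be in its denominator, so the figure is not part of the finding.

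**The reference side.** It is tempting to add that the expected proportion is not lowered in the same way, so that the whole comparison always favours the drug. The protocol does not say how the NAPPED probabilities are estimated or over what follow-up, so this cannot be checked.

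**Low stakes.** Section 11.1 states that there is no formal hypothesis testing, and this is a secondary variable. That is fair, and it limits the weight of the point.

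**Conclusion.** The point holds in a limited form. The simple proportion makes no allowance for unknown Week 72 status, and if such patients stay in the denominator, as the FAS default implies, the observed proportion and its upper limit are biased downward. The relative bias is about −5% with 10% unobserved and −10% with 20%. The chance of an upper limit below 30% at a true 30% stays at or below 2.5% with 10% unobserved, and rises to 3.1% (n=48) and 4.1% (n=60) with 20%.

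These sizes rest on assumed loss rates, uniform exit, constant hazard and exit unrelated to risk. Bias would be larger if patients left because surgery was imminent, or if the comparison were run before all patients in the denominator had reached Week 72; the protocol states neither. With few patients truly lost, the final analysis would be only mildly affected. The change is worth making because it is cheap and gives a better estimator for this comparison.

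**What to change.** In section 11.2.2.6, base the upper-limit comparison on the Kaplan-Meier cumulative incidence of the composite at Week 72 with its 95% confidence interval. Censor event-free patients at last confirmed contact, and compare with the expected proportion over the same 72 weeks. Use the exact binomial limit if follow-up is complete or if there are no events, since a log-log Kaplan-Meier interval is undefined with none. Keep the simple proportion as a descriptive figure.

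In sections 7.1.1 and 7.2.3, add vital status to the items gathered by telephone. In section 11.1, note that the 89% to 96% power assumes that every patient's 72-week status is known.

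The cost is about one sentence in each place, since the Kaplan-Meier analysis is already planned. The upper limit will be slightly higher, and so less favourable, when some patients are lost, and the stated power will then hold only for complete follow-up.

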11.2.2.7 Evaluation of Safety Variables

Safety data will be analyzed using descriptive statistics and summaries overall of SAEs, AEs, vital signs, clinical laboratory tests (hematology, clinical chemistry and urinalysis) and concomitant medication. Analyses will be performed using the full analysis set.

Summaries of AEs (coded according to the Medical Dictionary for Regulatory Activities (MedDRA) system organ class and MedDRA preferred term) will include:

- Overview of the incidence of TEAEs (TEAEs, Drug-related TEAEs, TEAEs leading to study discontinuation, and Treatment-emergent SAEs)
- TEAEs by system organ class (SOC) and preferred term
- Intensity of TEAEs by SOC and preferred term
- Drug-related TEAEs by SOC and preferred term
- TEAEs leading to study discontinuation by SOC and preferred term
- Treatment-emergent SAEs by SOC and preferred term

Concomitant medication use during the Treatment Period will be summarized by Anatomical Therapeutic Chemical (ATC) class and World Health Organization (WHO) preferred name.

Summaries of vital signs will be presented. For each visit, the actual results and the change from baseline, and the number and percentage of patients with potentially clinically significant (PCS) values observed post-baseline will be presented.

Summaries of clinical safety laboratory data will be presented. For each visit, the actual result and the change from baseline, and the number and percentage of patients with PCS values observed post-baseline will be presented.

Data listings will be provided for each patient for all safety parameters.

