
Evaluation of Safety Variables:
 
Safety data will be analyzed using descriptive statistics and summaries overall of SAEs, AEs, vital signs, clinical laboratory tests (hematology, clinical chemistry and urinalysis) and concomitant medication. Analyses will be performed using the full analysis set.
		

Sample Size Determination:
 
There is no formal hypothesis testing in this open label-study. Sample size for Cohort 1 was determined in Study A4250-005. For Cohort 1, patients will be enrolled following completion or participation of at least 12 weeks of Study A4250-005. The expected proportion of patients with at least one event, i.e., surgical bile diversion or liver transplantation or death, in untreated patients is expected to be high enough to be able to detect an improvement after A4250 treatment. If the expected proportion with at least one event is estimated to be 30% in the study population of Cohort 1, and then if the proportion of patients with at least one event during A4250 long-term treatment are shown to be only 10% in the study, the power is approximately 89% to 96% (1-sided test, alpha=2.5%) for a CI with upper boundary <30% based on a sample size of n=48 to 60. The sample size of 60 patients for Cohort 2 was estimated based on the availability of target patient population to evaluate the therapeutic benefit for those patients.
		

Date of the Protocol: 11 February 2022
		

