Based on the mode of action of A4250, an IBAT inhibitor, loose stools or diarrhea, and abdominal pain are expected AEs. Non-serious diarrhea and abdominal pain were reported in healthy volunteers and in the investigator-initiated PBC study and in one patient following single dose, but none following multiple dosing in the Phase 2 study in pediatric patients with pruritic cholestatic liver disease. Non-serious diarrhea, vomiting, and abdominal pain were observed in the Phase 3 study in pediatric patients with PFIC.

A4250 taken once daily (QD) at doses up to 200 µg/kg/day, as tested in the Phase 2 study A4250-003, and up to 120 µg/kg/day as evaluated in the Phase 3 study A4250-005, was overall well tolerated. Gastrointestinal (GI) treatment-emergent adverse events (TEAEs) including abdominal pain, abdominal discomfort and diarrhea or loose stool, were associated in time with the onset of the treatment effect of A4250. In general, these AEs were mild to moderate in nature and self-limiting, did not require treatment intervention and were not linked to the degree of reduction of serum bile acid or a rapid reduction in serum bile acid levels.

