Patients not meeting eligibility criteria may be re-screened after consultation with the Medical Monitor. Patients not fulfilling inclusion/exclusion criteria after 3 attempts are not allowed to rescreen.

³ As of Protocol Amendment 6.2 Sweden, patients entering Cohort 2 will start treatment at 40 µg/kg/day with the possibility to dose escalate to 120 µg/kg/day after 12 weeks if there is no improvement in pruritus based on investigator judgment.

Patients will have a minimum of 12 visits at the study site and 6 scheduled telephone contacts (see [Figure 1](#) and [Figure 2](#)) as follows:

- Visit 1: Screening/Inclusion Visit (Day 1; coincides with Visit 9 in Study A4250-005 for patients in Cohort 1)
- Visit 2: Week 4
 - Telephone contact 1: Week 8
- Visit 3: Week 12
 - Telephone contact 2: Week 18
- Visit 4: Week 22
- Visit 5: Week 24
 - Telephone contact 3: Week 30
- Visit 6: Week 36
 - Telephone contact 4: Week 42
- Visit 7: Week 46
- Visit 8: Week 48
 - Telephone contact 5: Week 54
- Visit 9: Week 60
 - Telephone contact 6: Week 66
- Visit 10: Week 70
- Visit 11: Week 72
- Visit 12: Follow-up Visit; Week 76

Additional clinic visits may be required for patients who need direct site assistance including, but not limited to, AE monitoring for safety maintenance.

Informed consent must be obtained prior to performing any study procedures. After signing the informed consent form (ICF), patients will be evaluated for study eligibility and considered enrolled in the study. For Cohort 1, patients who completed 24 weeks, or who withdrew after a minimum of 12 weeks of treatment with A4250 due to intolerable symptoms in Study A4250-005 and meeting all inclusion criteria and no exclusion criteria are eligible for this study. Patients who withdraw from A4250-005 due to a study drug related AE will not be eligible. For Cohort 2, patients meeting all inclusion criteria and no exclusion criteria are eligible for this study.

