7.2.1 Inclusion Criteria

Cohort 1:

1. Completion of the 24-week Treatment Period of Study A4250-005 or withdrawn from Study A4250-005 due to patient/caregiver judgment of intolerable symptoms after completing at least 12 weeks of treatment. Patients who withdraw from A4250-005 due to a study drug related AE will not be eligible.
2. Signed informed consent and assent as appropriate. Patients who turn 18 years of age (or legal age per country) during the study will be required to re-consent to remain on the study.
3. Patients expected to have a consistent caregiver for the duration of the study.
4. Caregivers (and age-appropriate patients) must be willing and able to use an eDiary device as required by the study.

Cohort 2:

1. A male or female patient of any age, with a clinical diagnosis of PFIC, including episodic forms (i.e., BRIC), and with a body weight ≥ 5 kg at Visit S-1.
2. Patient must have clinical genetic confirmation of PFIC.
3. Patients with PFIC, excluding BRIC, must have elevated serum bile acid concentration, specifically measured to be ≥ 100 $\mu\text{mol/L}$, taken as the average of 2 samples at least 7 days apart (Visits S-1 and S-2) prior to the Screening/Inclusion Visit (Visit 1).

4. Patients with PFIC, excluding BRIC, must have history of significant pruritus and a caregiver-reported observed scratching or patient-reported itching (for patients >18 with no caregiver-reported observed scratching) in the eDiary average of ≥ 2 (on 0 to 4 scale) in the 2 weeks prior to the Screening/Inclusion Visit (Visit 1).
5. Patients with episodic forms of PFIC (i.e., BRIC) must have an emerging flare characterized by clinically significant pruritus and elevated serum bile acid levels/cholestasis as judged by the investigator.
6. Patient and/or legal guardian must sign informed consent (and assent) as appropriate. Patients who turn 18 years of age (or legal age per country) during the study will be required to re-consent in order to remain in the study.
7. Age appropriate patients are expected to have a consistent caregiver for the duration of the study.
8. Caregivers and age-appropriate patients (≥ 8 years of age, if able) must be willing and able to use an eDiary device as required by the study.

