10 ASSESSMENT OF SAFETY

The timing and frequency of safety assessments are described in [Section 7.1.2](#) and [Section 7.1.3](#).

The primary safety analysis for this study will include the incidence of total treatment-emergent adverse events (TEAE) and TEAEs categorized by causality, severity, and seriousness assessments.

Trends in safety will also be evaluated for the following assessments:

- Physical examinations
- Concomitant medications
- Vital signs
- Laboratory test results (including clinical chemistry, hematology, urinalysis, AFP, vitamins A, E, and 25-hydroxy vitamin D, and INR)
- Abdominal ultrasound
- Discontinuations due to AEs

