10.1.2 Recording of Adverse Events

It is the investigator's responsibility to assess whether each untoward event is a clinically significant worsening from baseline, thereby considered an AE. For all AEs, the severity, seriousness, and causality to study drug for each AE as outlined in [Section 10.1.1](#) will be assessed and recorded in the eCRF.

All serious and non-serious AEs are collected once the caregiver/patient has signed the ICF and until the post-treatment follow-up (Visit 12), 28 days after the last dose of study drug.

Any AEs or SAEs that are unresolved at the patient's last AE assessment in the study are followed up by the investigator until resolution or stabilization up to the database lock and recorded in the eCRF. Albireo retains the right to request additional information for any patient with ongoing AE(s) or SAE(s) at the end of the study.

TEAEs that are ongoing at time of discontinuation will be followed up until week 72 by telephone calls every 3 months. No new AEs will be recorded after the patient has permanently discontinued study drug.

TEAEs are defined as any AE that occurs after dosing (Day 1), including new AEs or the worsening of an event after the first dose.

If there is a clinically significant deterioration of a laboratory value/vital sign or other routine study assessment that is associated with a diagnosis, the clinical diagnosis will be reported as an AE and the associated signs and symptoms will be considered additional information unless the sign or symptom is more severe than expected given the diagnosis. For example, if an investigator diagnoses a study patient with hepatitis during the study period, hepatitis would be considered the AE and the concomitant signs and symptoms of abdominal pain, vomiting, and elevated ALT and AST would not be reported separately unless, in the opinion of the investigator, one of these signs or symptoms is more severe than expected and therefore a separate AE assessment is indicated.

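### The protocol does not settle whether adverse-event tables are split by prior A4250 exposure; a pooled figure alone would probably understate gastrointestinal events that occur at the start of treatment

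*Protocol*

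**What the plan says.** Protocol Section 10 names the main safety measure: "The primary safety analysis for this study will include the incidence of total treatment-emergent adverse events (TEAE". Section 11.2.2.7 gives its form: "Safety data will be analyzed using descriptive statistics and summaries overall of SAEs, AEs, vital signs, clinical laboratory tests". The safety paragraph of the synopsis agrees: "Safety data will be analyzed using descriptive statistics and summaries overall of SAEs, AEs, vital signs". Both use the full analysis set, defined in Section 11.2.1 as "all patients who received at least 1 dose of study drug in Study A4250-008", so both cohorts are in it.

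Section 10.1.2 opens the counting window: "TEAEs are defined as any AE that occurs after dosing (Day 1". Only new events, or worsening after the first dose, qualify. Section 7.1.1 fixes that day for rollover patients: "Screening/Inclusion Visit (Day 1; coincides with Visit 9 in Study A4250-005 for patients in Cohort 1".

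Two further statements matter. Section 7.2.1 says of Cohort 1: "Patients who withdraw from A4250-005 due to a study drug related AE will not be eligible". Section 5.3.1 says that gastrointestinal TEAEs, including abdominal pain and diarrhea, "were associated in time with the onset of the treatment effect of A4250".

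Section 11.2.2.1 (General Principles) lists groups for descriptive statistics: the cohorts, Cohort 1 by Study 005 arm, the two active 005 arms together, and placebo rollovers combined with Cohort 2 excluding BRIC (the episodic form). The synopsis carries the same list under its heading for the primary efficacy variables.

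**The concern.** The full analysis set mixes two kinds of patient. Those who took A4250 in Study 005 arrive at Day 1 of Study 008 after up to 24 weeks on drug, and the ones who left 005 for a drug-related event have been removed. Placebo rollovers and Cohort 2 start A4250 at or near Day 1. If gastrointestinal events cluster around the start of effect, as the protocol reports, the first group has largely passed its period of highest risk before counting begins.

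A single pooled incidence then describes neither group. A reader would naturally take it as what a new patient should expect, and for diarrhea and abdominal pain it would probably be too low. Whether the reader sees anything else depends on whether the groups in Section 11.2.2.1 apply to the safety tables, and the protocol does not settle that.

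**Working it through.** **Does the grouping list reach safety?** The statements point in different directions:

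| Place in protocol | What it indicates |
|---|---|
| 11.2.2.1 General Principles | Groups apply to descriptive statistics; no limit to efficacy stated |
| Synopsis, statistical methods | Same list, placed under primary efficacy |
| 11.2.2.4 Disposition | Overall and by cohort |
| 11.2.2.3 Baseline | Cohort 2 also by diagnostic subgroup |
| 11.2.2.7 Safety, and synopsis safety paragraph | Overall only |
| 11.2.2.8 Exposure and compliance | Presented overall |

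Read through 11.2.2.1, safety is split by 005 arm. Read through 11.2.2.7 and the synopsis, it is not. Both readings are tenable.

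**How much would a pooled figure differ?** The protocol states no safety incidence for the pooled set, so there is no figure to reproduce. The effect can be shown as a weighted mean.

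Inputs:
- Total about 120 patients, of whom about 60 are in Cohort 1 (synopsis).
- Pre-exposed patients, E: the protocol gives no 005 allocation. Assumed 1/2, 2/3 or 3/4 of Cohort 1, that is 30, 40 or 45.
- Relative rate r of an onset-type event in pre-exposed versus naive patients: not in the documents. Shown from 0 to 1.
- All other patients are treated as A4250-naive at Day 1.

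Pooled rate as a fraction of the naive rate = ((120 − E) + E × r) / 120.

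| E | r = 0 | r = 0.5 | r = 1 |
|---|---|---|---|
| 30 | 90/120 = 75% | 105/120 = 87.5% | 100% |
| 40 | 80/120 = 66.7% | 100/120 = 83.3% | 100% |
| 45 | 75/120 = 62.5% | 97.5/120 = 81.3% | 100% |

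For illustration, with E = 40 and an assumed naive rate of 30%, the pooled rate is 20.0% at r = 0, 22.5% at r = 0.25, 25.0% at r = 0.5 and 30.0% at r = 1.

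**Would a split by cohort alone be enough?** No, because the Cohort 1 total also mixes placebo and active rollovers. Within Cohort 1 the fraction is ((60 − E) + E × r) / 60. At r = 0.5 it is 45/60 = 75% for E = 30 and 37.5/60 = 62.5% for E = 45. The useful division is prior exposure.

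**The case against.** The strongest reply is that Section 11.2.2.1 already provides the split. It sits under General Principles, it governs descriptive statistics, and 11.2.2.7 says that safety is analysed descriptively. Where the authors meant efficacy only, as for the separate presentation of BRIC, they said so in that section. The list names a pooled active-rollover group and a group of placebo rollovers plus Cohort 2 excluding BRIC, which is nearly the contrast wanted. Summarising overall need not mean only overall, and table columns are often left to the statistical analysis plan, which is not shown.

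Much of this stands. A reader might infer that the protocol plans nothing but a pooled column; the documents do not support that. They do leave the matter open, because the synopsis ties the list to efficacy and the safety wording differs from that for disposition. Even if the list applies, its nearly naive group leaves out BRIC patients, and Section 11 plans no count from the first A4250 dose. Section 5.3.2 mentions an integrated analysis of 005 and 008, but Section 11 does not include one.

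Other limits also stand:
- A reader might infer that every rollover patient had already tolerated A4250. Placebo rollovers are naive, patients moving from 40 to 120 µg/kg/day are new to the higher dose, and Section 7.2.1 admits patients who left 005 for intolerable symptoms after at least 12 weeks. The last two groups could move r towards 1.
- A reader might extend the point to all drug-related events. Section 5.3.1 ties only gastrointestinal events to onset. The most common drug-related events in children were rises in ALT, AST and bilirubin (Section 5.2.2), and nothing says that these cluster at onset.
- Counting from Day 1 of the extension is ordinary practice and fits an objective of long-term safety. It is no error in itself.

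**Conclusion.** The point holds as a conflict to be resolved. Section 11.2.2.7 and the synopsis specify overall safety summaries, while 11.2.2.1 can be read as requiring groups by cohort and prior arm. If only the pooled figure is reported, the incidence of onset-related gastrointestinal events is likely to be lower than in A4250-naive patients.

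The direction rests on the protocol's own account of timing and on its entry rules. The size cannot be derived: it needs the number of pre-exposed patients and the relative rate, and the documents give neither. Under the assumptions shown, the pooled rate lies between about 63% of the naive rate and no dilution at all. A reader might infer a firm shortfall from any one cell of the table; the documents support only the range.

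**What to change.** State in Section 11.2.2.7, and match in the synopsis, that TEAE tables are presented by prior exposure using the 11.2.2.1 groups:

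- A4250-naive: Cohort 1 placebo rollovers plus Cohort 2, with BRIC patients included or shown alongside.
- Treated with A4250 in Study 005: pooled, and separately for the 40-to-120 and 120-to-120 arms.
- The overall column kept next to these.

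For the previously treated, add a supportive TEAE summary counted from the first A4250 dose in Study 005, with exposure time, so that early events are visible.

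The cost is extra table columns from data already held in 005 and 008, and a short addition to the text. No new procedures are needed. The naive incidence may look less favourable than the pooled one.
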